8. PHARMACEUTICAL INFORMATION

A list of the adverse events and potential risks associated with the agents administered in this study can be found in the investigative drug brochure.

8.1 Pembrolizumab

8.1.1 Description

Pembrolizumab (MK-3475) is a humanized anti-PD-1 mAb of the IgG4/kappa isotype with a stabilizing S228P sequence alteration in the fragment crystallizable (Fc) region. MK-3475 binds to human PD-1 and blocks the interaction between PD-1 and its ligands. The theoretical molecular weight of the polypeptide is 146,288 Da and its theoretical pI is 7.5. The parental murine anti-human PD-1 antibody (hPD-1.09A) was produced by immunizing mice with hPD-1 DNA. The MK-3475 antibody was generated by humanization of the parental antibody by the Medical Research Council (Cambridge, UK) using complementarily-determining region (CDR) grafting technology (U.S. Patent No. 5,225,539). The gene segments encoding the variable heavy and light chains of MK-3475, as well as human IgG4, were codon-optimized, synthesized, and ligated into a vector.

A single expression plasmid, pAPD11V1-GA was constructed for the expression of both the heavy and light antibody chains of MK-3475. The nucleotide sequences encoding the heavy and light chains, along with their respective

CONFIDENTIAL

This document is confidential. Do not disclose or use except as authorized.

promoters and poly A signal sequences have been confirmed by DNA sequence analysis. The pAPD11V1-GA expression vector was subsequently used to transfect CHO-DXB-11 cells for the development of the MK-3475-producing cell line.

The theoretical molecular weight of the polypeptide is 146,288 Da and its theoretical pI is 7.5. Pembrolizumab exhibits linear pharmacokinetics at dose levels of clinical relevance (1-10 mg/kg). It exhibits low clearance and limited volume of distribution that is typical for therapeutic antibodies. Mean estimated t_{1/2} values are 14.1-21.6 days.

The nomenclature of pembrolizumab is provided in the table below:

The nomenclature of pembrolizumab is provided in the table below:

Code Name	MK 3475 (Anti-PD-1)
Other Code Name	SCH 900475 (Anti-PD-1)
Chemical Name	Humanized X PD-1_mAb (H409A11) IgG4
CAS Number	1374853-91-4
CAS Name	Anti-(human protein PDCD1 (programmed cell death 1)) immunoglobulin G4 (human-Mus musculus monoclonal heavy chain) disulfide with human-Mus musculus monoclonal light chain, dimer
Generic Name	Not available
Commercial Name	Pembrolizumab

8.1.2 Form

The investigator shall take responsibility for and shall take all steps to maintain appropriate records and ensure appropriate supply, storage, handling, distribution and usage of investigational product in accordance with the protocol and any applicable laws and regulations.

Pembrolizumab is supplied as a clear to opalescent solution that is essentially free of extraneous particles and may contain proteinaceous particulates. One dosage form of pembrolizumab will be provided by Merck in Type I glass vials intended for single use only as summarized in the following table:

Product Name & Potency	Dosage Form
Pembrolizumab 100 mg/ 4mL	Solution for Injection

Pembrolizumab solution for infusion is a sterile, non-pyrogenic, aqueous, preservative-free solution. Pembrolizumab solution for infusion contains an excess fill of 6.25 mg (equivalent to 0.25 mL solution) to ensure the recovery of label claim of 100 mg pembrolizumab per vial (equivalent to

CONFIDENTIAL

This document is confidential. Do not disclose or use except as authorized.

4.0 mL of solution).

8.1.3 Storage and Stability

As specified in the Pharmacy Manual for pembrolizumab as provided by the Overall PI.

Clinical supplies must be stored in a secure, limited-access location under the storage conditions specified on the label.

8.1.4 Compatibility

The following infusion set materials are compatible with Pembrolizumab

- PVC infusion set that is plasticized using Di-2-ethylhexyl Terephthalate DEHP
- PVC and tri-(2-ethylhexyl) trimellitate (TOTM) infusion set
- Polyethylene lined PVC infusion set
- Polyurethane
- Polybutadiene A sterile, non-pyrogenic, low-protein binding 0.2 to 5 µm in-line filter made of polyethersulfone (PES) or polysulfone must be used during administration to remove any adventitious particles. If the infusion set does not contain a 0.2 to 5 µm in-line filter, it is recommended to use a 0.2 to 5 µm add-on filter which may contain an extension line (the materials of the extension line and filter should be as mentioned above).

A sterile, non-pyrogenic, low-protein binding 0.2 to 5 µm in-line filter made of polyethersulfone (PES) or polysulfone must be used during administration to remove any adventitious particles. If the infusion set does not contain a 0.2 to 5 µm in-line filter, it is recommended to use a 0.2 to 5 µm add-on filter which may contain an extension line (the materials of the extension line and filter should be as mentioned above).

8.1.5 Handling

Receipt and dispensing of trial medication must be recorded by an authorized person at the trial site.

Clinical supplies may not be used for any purpose other than that stated in the protocol.

CONFIDENTIAL

This document is confidential. Do not disclose or use except as authorized.

8.1.6 Availability

Pembrolizumab will be supplied free-of-charge from Merck.

8.1.7 Administration

Pembrolizumab will be administered as a 30 minute IV infusion using an infusion pump (treatment cycle intervals may be increased due to toxicity as described in Section 6). Sites should make every effort to target infusion timing to be as close to 30 minutes as possible. However, given the variability of infusion pumps from site to site, a window of -5 minutes and +10 minutes is permitted (i.e., infusion time is 30 minutes: -5 min/+10 min). Attach the infusion line to the pump and prime the line, either with normal saline (at least 25 mL) or with infusion solution as per local SOP, before starting the infusion. Maximum infusion rate should not exceed 6.7 ml/min through a peripheral or indwelling catheter. Use 30 mL normal saline to flush the infusion line at the end of the infusion if institutional guidelines allow.

Unused infusion solution should not be used for another infusion of the same participant or different participant.

DO NOT administer the product as an intravenous push or bolus.

DO NOT combine, dilute or administer it as an infusion with other medicinal products.

A central line is not required for Pembrolizumab administration, but may be used if available.

8.1.8 Ordering

Participating Institutions will order their own investigational agent (Pembrolizumab) directly from Merck using the Drug Supply Request Form. Please allow for 3 weeks for drug to arrive after the order is submitted. The Participating Institution will ensure that the pharmacy will be able to receive and store the agent according to state and federal guidelines. The local IRB should be kept informed of who will supply the agent (i.e., Merck pharmaceuticals Inc.) so that any regulatory responsibilities can be met in a timely fashion.

8.1.9 Accountability

The investigator is responsible for keeping accurate records of the clinical supplies received from Merck or designee, the amount dispensed to and returned by the subjects and the amount remaining at the conclusion of the trial.

CONFIDENTIAL

This document is confidential. Do not disclose or use except as authorized.

8.1.10 Destruction and Return

Upon completion or termination of the study, all unused and/or partially used investigational product will be destroyed at the site per institutional policy. It is the Investigator's responsibility to arrange for disposal of all empty containers, provided that procedures for proper disposal have been established according to applicable federal, state, local and institutional guidelines and procedures, and provided that appropriate records of disposal are kept.

8.2 Dabrafenib mesylate (GSK2118436B) (NSC 763760)

8.2.1 **Chemical Name:** N-{3-[5-(2-Amino-4-pyrimidinyl)-2-(1,1-dimethylethyl)-1,3-thiazol-4-yl]-2-fluorophenyl}-2,6-difluorobenzene sulfonamide, methanesulfonate salt

8.2.2 **Other Names:** GSK2118436, GSK2118436A (free base), Tafinlar

8.2.3 **Classification:** BRAF inhibitor

8.2.4 **CAS Registry Number:** 1195768-06-9

8.2.5 **Molecular Formula:** $C_{23}H_{20}F_3N_5O_2S_2 \cdot CH_4O_3S$

8.2.6 **M.W.:** 615.68 (mesylate salt)

8.2.7 **Mode of Action:** Dabrafenib mesylate (GSK2118436B) is a potent and selective BRAF kinase inhibitor. This inhibition suppresses downstream activity of pERK, a biomarker, and has antiproliferative activity against BRAF mutant tumors. The mode of action is consistent with ATP-competitive inhibition.

8.2.8 **How Supplied:** Dabrafenib mesylate (GSK2118436B) capsules will be supplied commercially.

- 50 mg capsule is Swedish orange, size 2 with markings of four black bars.
- 75 mg capsule is pink, size 1 with markings of four black bars.

Capsule excipients include microcrystalline cellulose, magnesium stearate (vegetable source), colloidal silicon dioxide. Shell composition consists of an opaque hypromellose capsule, composed of red iron oxide (E172), titanium dioxide (E171), and hypromellose (E464). Four black bars are printed on the hypromellose capsules using black ink. The black ink contains black iron oxide (E172), shellac, propylene glycol, and ammonium hydroxide.

CONFIDENTIAL

This document is confidential. Do not disclose or use except as authorized.

8.2.9 **Storage:** Store between 15°C to 30°C (59°F to 86°F).

8.2.10 **Stability:** Shelf-life studies of dabrafenib mesylate (GSK2118436B) are ongoing.

8.2.11 **Route of Administration:** Oral administration. Take dabrafenib mesylate (GSK2118436B) 1 hour prior or 2 hours after a meal. If a dose is missed, it should not be taken if it is less than 6 hours until the next dose.

8.2.12 **Potential Drug Interactions:** *In vitro* studies show that dabrafenib mesylate (GSK2118436B) induces CYP3A4, 2B6, 2C9,8, 2C9, and 2C19 enzymes. Use caution in patients who are taking substrates that are metabolized in these enzyme pathways.

Dabrafenib mesylate (GSK2118436B) metabolism appears to be mediated by CYP3A4 and CYP2C8. Use caution if strong inducers or inhibitors of CYP2C8 or 3A4 are co-administered with dabrafenib.

Patients should avoid ingesting the fruit or juice of Seville oranges, grapefruit, pummelos, exotic citrus fruits, or grapefruit hybrids for at least 24 hours prior to the start of dosing because of inhibition of intestinal CYP3A4.

Dabrafenib solubility is pH-dependent and experiences decreased solubility at higher pH. Use caution in patients who are taking drugs that elevate gastric pH due to the theoretical risk of decreasing oral bioavailability of dabrafenib.

8.2.13 Availability

Dabrafenib mesylate (GSK2118436B) is FDA-approved for the treatment of unresectable or metastatic BRAF-mutant melanoma. It will be used at its standard dose and schedule for its indicated purpose. Commercial dabrafenib will be used throughout the study and obtained from specialty pharmacies and with coverage provided by participant's individual health insurance.

8.3 Trametinib dimethyl sulfoxide (GSK1120212B) (NSC 763093)

8.3.1 **Chemical Name (IUPAC):** equimolecular combination of N-(3-{3-cyclopropyl-5-[(2-fluoro-4-iodophenyl)amino]-6,8-dimethyl-2,4,7-trioxo-3,4,6,7-tetrahydropyrido[4,3-d]pyrimidin-1(2H)-yl}phenyl)acetamide with (methylsulfinyl)methane

8.3.2 **Other Names:** trametinib, GSK1120212, JTP-74057, JTP-78296, JTP-75303, Mekinist

CONFIDENTIAL

This document is confidential. Do not disclose or use except as authorized.

8.3.3 **CAS Registry Number:** 1187431-43-1

8.3.4 **Classification:** MEK inhibitor

8.3.5 **Molecular Formula:** $C_{26}H_{23}FIN_5O_4 \cdot C_2H_6OS$

8.3.6 **M.W.:** 693.54 (dimethyl sulfoxide solvate), 615.41 (anhydrous parent)

8.3.7 **Approximate Solubility:** Trametinib dimethyl sulfoxide is almost insoluble in water (<0.0001 mg/mL at 25° C)

8.3.8 **Mode of Action:** Trametinib dimethyl sulfoxide is a reversible, highly selective, allosteric inhibitor of mitogen-activated extracellular signal regulated kinase 1 (MEK1) and MEK2. Tumor cells commonly have hyperactivated extracellular signal-related kinase (ERK) pathways in which MEK is a critical component. Trametinib dimethyl sulfoxide inhibits activation of MEK by RAF kinases and MEK kinases.

8.3.9 **Description:** Trametinib dimethyl sulfoxide is a white to almost white powder.

8.3.10 **How Supplied:** Tablets will be supplied commercially.

The tablet core contains mannitol, microcrystalline cellulose, hypromellose, croscarmellose sodium, magnesium stearate (non-animal), colloidal silicon dioxide, and sodium lauryl sulfate.

- 0.5 mg tablets are white or yellow, modified oval, biconvex and film-coated. Aqueous film coating consists of Opadry Yellow 03B120006 (hypromellose, titanium dioxide, polyethylene glycol, iron oxide yellow).
- 2 mg tablets are pink, round, biconvex and film-coated. Aqueous film coating consists of Opadry Pink YS-1-14762-A, hypromellose (titanium dioxide, polyethylene glycol, polysorbate 80, iron oxide red).

8.3.11 **Storage:** Store tablets at 2°C - 8°C (36°F - 46°F) in the original bottle. Bottles should be stored in the manufacturer's package carton for light protection. Protect from moisture. For additional storage instructions, please refer to package insert.

8.3.12 **Stability:** Shelf life studies of trametinib dimethyl sulfoxide are ongoing.

8.3.13 **Route of Administration:** Oral. Take by mouth on an empty stomach, either 1 hour before or 2 hours after a meal. If a dose is missed, it should not be taken if it is less than 12 hours until the next dose.

8.3.14 **Potential Drug Interactions**

CONFIDENTIAL

This document is confidential. Do not disclose or use except as authorized.

In vitro studies suggest that trametinib dimethyl sulfoxide is not a substrate of CYP enzymes or of human Pgp, BCRP, OATP1B1 or OATP1B3 transporters.

Trametinib dimethyl sulfoxide is a weak CYP2C8 inhibitor and weak CYP3A4 inducer. Drug-drug interactions with sensitive substrates of 2C8 and 3A4 are not anticipated.

8.3.15 Availability

Trametinib dimethyl sulfoxide (GSK1120212B) is FDA-approved for the treatment of unresectable or metastatic BRAF-mutant melanoma. It will be used at its standard dose and schedule for its indicated purpose. Commercial trametinib will be used throughout the study and obtained from specialty pharmacies and with coverage provided by participant's individual health insurance.

9. BIOMARKER, CORRELATIVE, AND SPECIAL STUDIES

9.1 Collection of Specimen(s)

Tumor biopsies are required be performed in all patients for both cohorts at four time points (as all patients are enrolled onto the first Stage of the Simon 2-stage design):

1. Prior to commencing MTT
2. Following 2-week MTT lead-in
3. Following 6-weeks of combined pembrolizumab with MTT (if feasible)
4. A biopsy at the time of disease progression will also be performed (this is optional)

Multiple cores will be obtained and/or sufficient tumor excised at each biopsy time-point, assuming that it is safe to do so (e.g. patients with rapid responses may have very little tumor to biopsy safely at the latter time points). Core biopsies or portions of the excised tumor will be processed with the following hierarchy in mind:

1. DNA/RNA/protein extraction ([name])
2. Disaggregation and flow cytometry ([name])
3. FFPE ([name])
4. Single-cell RNA seq of T cells ([name])
5. Single-cell RNA seq of tumor cells ([name])

Analysis will then be carried out to compare changes seen longitudinally and to determine if those changes are associated with improved outcomes to therapy with study treatment. Most of this work will be exploratory in nature, as analysis

CONFIDENTIAL

This document is confidential. Do not disclose or use except as authorized.

such as the technology for single-cell sequencing of tumor and T-cells is emerging and no data is presently available to inform how these analyses might be used to help predict which patients are most likely to benefit from single-agent or combination therapy. However, based on previous work, there are two assays that will be incorporated into a predictive model, PD-L1 expression by immunohistochemistry (IHC) and immuno-sequencing (immunoSEQ) using the Adaptive Biotechnologies platform.

9.1.1 Handling of Specimens(s)

As described above, four cores will be obtained and fixed. The SOP for collection, handling, and processing is attached (Appendix C). Samples will either be stored at the individual sites and sent in batch at the time of planned correlative study analysis or sent to and stored at the [name] Laboratory at MGH. FFPE samples will be stored at room temperature. Frozen samples will be stored in a -80 degree freezer.

9.2 PD-L1 Immunohistochemistry

Immunohistochemistry for PD-L1 and CD8 will be performed in [name] laboratory using a monoclonal anti-PD-L1 antibody (Clone E1L3N, Cell Signaling Technologies; Danvers, MA) and a CD8 monoclonal antibody (4B11, RTU, Leica Biosystems, Buffalo Grove, IL), respectively, with an automated stainer (Bond Rx, Leica Microsystems, Buffalo Grove, IL). As there is no recognized standard PD-L1 scoring protocol, we will define PD-L1 positivity as membranous +/- cytoplasmic staining of tumor cells of any intensity using two different cut-offs ($\geq 1\%$ and ≥ 5 tumor cells) since both have been associated with clinical benefit to PD-1 pathway blockade in melanoma.

CONFIDENTIAL

This document is confidential. Do not disclose or use except as authorized.

9.3 **Adaptive Biotechnologies immunoSEQ**

FFPE specimens (or isolated tumor DNA) and frozen PBMC samples will be shipped to Adaptive Biotechnologies.

Samples sent to Adaptive will be handled in accordance with Adaptive SOPs. All arriving packages will be opened the same day they arrive and inspected thoroughly for correct labeling and packaging integrity. Adaptive will perform “survey level” sequencing on each tissue sample and “deep level” sequencing on each of the PBMC derived gDNA samples provided. As part of these analyses, Adaptive uses a proprietary assay for the amplification and massive parallel sequencing of millions of CDR3 regions in the T cell receptor beta gene (TCRB) using a multiplex PCR amplification across the VDJ junction of rearranged TCRB.

Using Adaptive’s unique capacity to perform next generation sequencing of T-cell receptors for this study, a large amount of data will be generated using tissue specimens and PBMC samples from all collection time points. In addition to the immunoSEQ Analyzer software, which is available to all of Adaptive clients to aid in data analysis and visualization, Adaptive can directly involve its computational biology and biostatistics personnel in the data analysis.

9.4 **Tumor Microenvironment Assessment**

Tumor microenvironment assessment will be performed in collaboration with [name]. At least two biopsies will be earmarked for this work and will be sent to [name] laboratory.

To determine how the tumor cells are modulated during MTT alone, anti-PD1 plus MTT and anti-PD1 monotherapy combination, we will use single-cell and bulk RNA-seq, whole exome, etc. to assess the evolution of tumor cells during therapy. Sequential biopsies will provide a means to analyze evolution of tumor cell responsiveness and resistance to therapy

To determine how immune cells in the tumor microenvironment are modulated during MTT alone, anti-PD1 plus MTT and anti-PD1 monotherapy combination, we will use single-cell and bulk RNA-seq, and assays to compare immune cell function (e.g., T cell activation vs. exhaustion using cellular immunologic assays, as well as analysis of phosphoproteins and ubiquitination signaling) in temporal biopsies. These studies should reveal how anti-tumor immunity is modulated during the lead-in phase of the clinical trial with MTT, during MTT and anti-PD1 combination therapy and during subsequent anti-PD1 monotherapy.

9.5 **Pharmacodynamic Studies**

CONFIDENTIAL

This document is confidential. Do not disclose or use except as authorized.

9.5.1.1 MITF

Biopsies will be obtained in patients

9.5.1.2 Blood-based BRAF assay

To explore the value of pretreatment BRAF level in predicting response to dabrafenib, trametinib, and Pembrolizumab, we will test isolated PBL and serum samples obtained prior to commencement of therapy. RNA will then be isolated from PBL and serum and BRAF^{V600} analysis will be performed as described in Figure 2.4.1. Quantitative analysis will be performed and levels will be reported in ng/uL. Two categories of levels will be analyzed, based on our previous data, those with values >900 ng/uL and \leq 900 ng/uL.

To explore the pharmacodynamic effects of dabrafenib, trametinib, and Pembrolizumab therapy on peripheral blood BRAF^{V600} mutation detection, we will serial test isolated PBL and serum samples. RNA will then be isolated from PBL and serum and BRAF^{V600} analysis will be performed as described in Figure 2.4.1. Patients will have quantitative analysis before and baseline values will be in ng/uL. Peripheral blood will be drawn pre-treatment, on Day 15 of the first cycle of treatment, and then on Day 1 of every subsequent cycle of therapy. Pre- and on-treatment BRAF^{V600} levels will be compared, and a blood-based response will be defined as a 50% or more decrease in signal based on acrylamide gel analysis. A blood-based progression will be defined as a doubling in signal based compared with nadir level on acrylamide gel analysis. A comparison of blood-based response or progression (>50% improvement vs. \leq 50% improvement; or 100% increase vs. < 100% increase) with clinical response (CR/PR by RECIST1.1) and clinical progression (PD) will then be performed to assess concordance between changes over time with our assay and with imaging.

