13.2 Sample Size, Accrual Rate and Study Duration

The total sample size for this study is 50 patients (25 patients per cohort). At an anticipated accrual rate of 2 patients per month, enrollment is expected to be completed in approximately two years.

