13.5 Analysis of Correlative Measures

Analysis of MTT induced changes on T-cell clonality / PDL1 expression and correlation with clinical benefit. To investigate whether MTT-associated changes following a brief course of MTT can predict who will benefit from the addition of anti-PD1 therapy, assessments will be based on: (a) clonality of tumor-infiltration lymphocytes (TILs), and (b) PD-L1 IHC. TIL clonality is a term used to quantify the diversity of clones and frequency of any given clone. It is calculated by ImmunoSeq Adaptive Biotechnologies software using a clonality score, defined as $[1 - (\text{entropy}) / \log_2(\# \text{ of productive unique sequences})]$, where the entropy term takes into account the varying clone frequencies of TILs. A maximally diverse population, where every sequence is represented one time, is associated with a clonality score of zero, and a perfectly monoclonal population with a clonality score of one. Assessment times will be pre-treatment and after the 2-week MTT lead-in. Each cohort will be investigated separately.

To investigate the hypothesis that there will be an increase in TIL clonality after MTT lead-in, the overall changes in clonality of TILs after MTT will be expressed as a fold-change (2-week/pre) and compared with unity using a Wilcoxon signed-rank test with 80% power, and a 0.1, two-sided significance level. For a range of standard deviations of the fold-change between 0.8 and 1.2, we will be able to detect effect sizes between 1.4 and 1.65 for this comparison. We will further refine this question to address whether increases in clonality are related to response. Clones that comprise the largest percentage of the total T-cell population after MTT lead-in will be identified and sorted by frequency. The percentage of the overall T-cell population included in the top 5% of clones will

be compared according to response (achieving/not achieving clinical benefit) using Wilcoxon rank-sum tests. If the observed CBR is 0.75, resulting in 19 patients with clinical benefit and 6 without, a Wilcoxon rank-sum test with 0.1, two-sided significance level will have 80% power to detect a difference in percentage T-cells that is approximately 1.3 times the common standard deviation. Similar analyses will be performed for the top 2.5% or 1% of clones.

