To assess if changes in clonality after MTT lead-in are associated with infiltration by new TIL clones, we will compare pre-treatment and post-MTT biopsies to identify clones that were absent from the pre-treatment biopsies, and summarize the percentage of individual clones that were identified to be new. This will be assessed for all patients in a cohort using Wilcoxon signed-rank tests, and according to clinical response using Wilcoxon rank-sum tests. In additional analyses, the percentage of pre-existing clones, rather than new clones, will be compared according to response to see if patients with high proportions of pre-existing clones after MTT lead-in exhibit a better response than patients with low proportions.

For PD-L1 expression, patients will be classified, retrospectively, into two subgroups defined by clinical benefit at 24 weeks. Fold-changes in PD-L1 IHC (2-week/pre) will be compared for patients achieving/not achieving clinical benefit using Wilcoxon rank-sum tests. If the observed CBR is 0.75, resulting in group sizes of 19 and 6, a Wilcoxon rank-sum test with 0.1, two-sided significance level will have 80% power to detect a difference in fold-changes that is approximately 1.3 times the common standard deviation.

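### Pretreatment blood BRAF is measured in ng/uL but planned as a predictor of response only as above versus at or below 900 ng/uL, which discards information if the relation is graded

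*Combined protocol and SAP*

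**What the plan says.** All references are to the combined protocol and SAP.

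- **Aim** (section 9.5.1.2, Blood-based BRAF assay): "To explore the value of pretreatment BRAF level in predicting response to dabrafenib, trametinib, and Pembrolizumab".
- **Scale** (same section): "Quantitative analysis will be performed and levels will be reported in ng/uL".
- **Form analysed** (same section): "Two categories of levels will be analyzed, based on our previous data, those with values >900 ng/uL and \leq 900 ng/uL". No comparison of the measured baseline level with response is described. CR/PR by RECIST 1.1 is given as the response definition only for the later comparison of serial changes.
- **Other candidate predictors** (section 13.5, Analysis of Correlative Measures): the share of T cells in the top clones and the fold-change in PD-L1 are compared on their full scale between patients with and without clinical benefit. For the first, "a Wilcoxon rank-sum test with 0.1, two-sided significance level will have 80% power to detect a difference in percentage T-cells" of about 1.3 common standard deviations. For PD-L1 the same is said: "Wilcoxon rank-sum test with 0.1, two-sided significance level will have 80% power to detect a difference in fold-changes" of that size. Blood BRAF does not appear in section 13.5.
- **Numbers** (section 13.2): "The total sample size for this study is 50 patients (25 patients per cohort"). A cohort that stops after stage 1 has 14 evaluable patients (section 13.1).

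**The concern.** A two-category split treats a patient just above 900 ng/uL the same as one far above it, and treats two patients just either side of it as different. If the chance of benefit changes gradually with the level, the split gives up power that the assay has already paid for. With 25 patients and about 6 without benefit, there is little power to spare.

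The result also depends on where 900 ng/uL falls in this population. The documents do not give the share of patients expected above it, and if most fall on one side there is almost no comparison to make. A useful predictor could be reported as uninformative because of the position of one inherited cut-off. The plan avoids this for its clonality and PD-L1 markers but not for this one.

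**Working it through.** **Inputs.** Nothing numerical is stated for blood BRAF beyond the cut itself. The setting is borrowed from section 13.5: "If the observed CBR is 0.75, resulting in group sizes of 19 and 6", a difference of 1.3 SD, and two-sided 0.10. Two further assumptions are mine: levels are normal on some scale with a shift between groups (a graded relation), and the cut may fall at a range of percentiles.

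**Step 1: reproduce the plan's figure for its other markers (80%).** The noncentrality is 1.3 × √(19 × 6 / 25) = 1.3 × 2.135 = 2.78. A t-test on 23 degrees of freedom has power 0.85. Allowing for Wilcoxon efficiency under normality (3/π) gives 0.84, and the minimum efficiency (0.864) gives 0.80, which matches the plan. Direct simulation of the rank-sum test on normal data gives about 0.82, used below.

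**Step 2: power after a split.** For a cut with a proportion q of all patients at or below it, solve [19·Φ(c − 1.3) + 6·Φ(c)] / 25 = q for c. The probabilities of being above the cut are p1 = 1 − Φ(c − 1.3) with benefit and p0 = 1 − Φ(c) without. At the median, c = 1.02, p1 = 0.61 and p0 = 0.15. Power is the sum, over all tables (a, b), of Bin(a; 19, p1) × Bin(b; 6, p0) for tables with p ≤ 0.10. Three tests are shown because the plan names none. Losses, in points against 0.82, are in brackets.

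| Patients at or below the cut | Chi-square, uncorrected | Boschloo exact | Fisher exact |
|---|---|---|---|
| 20% | 0.74 (8) | 0.72 (10) | 0.60 (22) |
| 30% | 0.75 (7) | 0.70 (12) | 0.64 (18) |
| 40% | 0.72 (10) | 0.64 (18) | 0.62 (20) |
| 50% | 0.68 (14) | 0.59 (23) | 0.56 (26) |
| 60% | 0.61 (21) | 0.56 (26) | 0.43 (40) |
| 70% | 0.46 (36) | 0.45 (37) | 0.19 (63) |

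The table takes patients with benefit to have the higher levels; if theirs are lower, mirror the percentiles. The maximum true size at a nominal 0.10 is 0.114 for chi-square, 0.096 for Boschloo and 0.06 for Fisher. Part of the Fisher loss is therefore the conservatism of that test, and chi-square is slightly flattered.

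**Step 3: vary the setting.**
- *Near-even outcome split* (13 against 12, 1.0 SD, as might arise with CR/PR): rank-sum 0.76. For cuts at 20–70%, Fisher loses 22–29 points and chi-square 12–29.
- *Cohort stopped at stage 1* (10 against 4, 1.3 SD): rank-sum only 0.58. For cuts at 20–50%, Fisher loses 8–16 points; chi-square loses at most 6 and at some cuts nothing.
- *True step exactly at the cut* (19 against 6, with 62% and 12% above it, and the level uninformative within each category): rank-sum 0.59, Fisher 0.66. Here the split is the better analysis.

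**The case against.** The strongest defence is that a cut-off carried forward from earlier data is fixed before the results are seen, and that testing whether it transfers is a legitimate question. The aim is exploratory. Blood BRAF is not among the objectives in sections 1.2–1.3 or the endpoints in section 13.1, and section 9.1 names only PD-L1 and immunoSEQ for the predictive model. The measured values will be reported, so a continuous analysis could be added later. All of this stands and limits the importance of the point. It does not remove it: the planned analysis still uses only two categories, and a continuous analysis chosen after the data are seen would lose the advantage of being prespecified.

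A reader might infer two stronger things. One is that the split costs at least about 20 points of power in this trial. The documents do not support that: 19 against 6, 1.3 SD and 0.10 belong to other markers, no test is named, and a floor near 20 points appears only with Fisher's test. The other is that 900 ng/uL is unfounded. The plan says "Two categories of levels will be analyzed, based on our previous data" and refers to a figure not available in the text, so the basis of the value cannot be judged either way.

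**Conclusion.** The point holds in a limited form. Section 9.5.1.2 plans a two-category analysis of a quantitative baseline marker and specifies no analysis on the measured scale, unlike the plan's treatment of its other predictors. If the relation with response is graded, information is lost.

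Under the borrowed setting, the loss from about 0.82 is 7–26 points for cuts between the 20th and 50th percentiles, depending on the test, and 36–63 points at the 70th percentile on the unfavourable side. There is no loss if the true relation is a step at 900 ng/uL. These figures assume normal levels and a cohort that reaches 25 patients. The assay is likely to be informative mainly in the BRAF-mutant cohort, which is also an assumption because the plan does not restrict it. The primary endpoint and the stopping rule are unaffected.

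**What to change.** In section 9.5.1.2, replace the two-category sentence with wording to this effect: the measured pretreatment BRAF level will be compared between patients with and without clinical benefit using a Wilcoxon rank-sum test at two-sided 0.10, as in section 13.5, as the main analysis of this marker; a comparison by CR/PR will be reported as supportive and exploratory; and the prespecified split at 900 ng/uL will be reported as a secondary descriptive result.

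This also supplies the test and the outcome definition that the section now lacks for the baseline level. It needs no new samples or assays and keeps comparability with the earlier data. The small cost is one additional exploratory test, which should be labelled as such.
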